6.4. Analysis of safety

6.4.1. Analysis of safety planned in the protocol

The analysis for safety will be based on the Exposed set. All safety analyses may also be performed by age strata (50-59, 60-69 and \geq 70 YOA), if deemed necessary.

When appropriate, tabulations will be presented overall and by time of occurrence relative to last vaccination (e.g. using windows such as Days 1 to 7, Days 1 to 30 and more than 30 days post-vaccination).

The results for the analysis of safety will be tabulated as follows:

- The number and percentage of subjects with at least one local solicited AE, with at least one general solicited AE, and with any solicited AE during the 7-day follow-up period with exact 95% CIs after each vaccine dose and overall by vaccination group will be provided;
- The percentage of subjects reporting each individual solicited local and general AE during the solicited 7-day follow-up period will be tabulated with exact 95% CI;
- For all solicited adverse events, the same tabulation will be performed for grade 3 solicited AEs and for solicited general AEs with relationship to vaccination;
- Number of days with each individual solicited local and general AE during the solicited 7-day follow-up period;
- The proportion of subjects with at least one report of unsolicited AE (containing both serious and non-serious unsolicited AEs) classified by the MedDRA Primary System Organ Class (SOC) and Preferred Terms (PTs) and reported up to 30 days after each vaccination will be tabulated with exact 95% CI;
- The same tabulation will be performed for grade 3 unsolicited AEs and for unsolicited AEs with a relationship to vaccination reported up to 30 days after each vaccination with exact 95% CI. The proportion of AEs resulting in a medically attended visit will also be tabulated;
- Total number/percentages of doses (per dose and overall) followed by AEs will be tabulated:
- Number of subjects with pIMDs will be tabulated;
- SAEs, including fatalities and withdrawal due to AE(s) will be described in detail.

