11. LIST OF FINAL REPORT TABLES, LISTINGS AND FIGURES

The TFL TOC provides the list of tables/listings and figures to be included in the study report.

The following group names will be used in the TFLs, in line with the T-domains:

Group order in tables	Group label in tables	Group definition for footnote	
1	Co-Ad	Dose 1: Prevenar 13 + HZ/su, Dose 2: HZ/su	
2	Control	Dose 1: Prevenar 13, Dose 2: HZ/su, Dose 3: HZ/su	

The following sub-groups will be used in the TFL, in line with the T-domains:

Table 6 Group Definitions to be used for the sub-group analysis by age (Analysis will be included in the clinical report)

Sub-group order in tables	Sub-group label in tables	Sub-group definition for footnote
1	50-59YOA	Subjects aged 50-59 years
2	60-69YOA	Subjects aged 60-69 years
3	≥70YOA	Subjects aged 70 years and over

YOA = Year of age

Please note that for table presentation in the sub-group analysis, the sequence maintained has to be each treatment group within each age sub-group.

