12. ANNEX 1 STANDARD DATA DERIVATION RULE AND STATISTICAL METHODS

12.1. Standard data derivation

12.1.1. Dose number

The study dose number is defined in reference to the number of study visits at which vaccination occurred. More specifically dose 1 refers to all vaccines administered at the first vaccination visit while dose 2 corresponds to all vaccinations administered at the second vaccination visit even if this is the first time a product is administered to the subject.

Associated dose: the associated dose for an event (AE, medication, vaccination) is the most recent study dose given before an event. In case the event takes place on the day a study dose is given, the associated dose will be that of the study dose, even if the event actually took place before vaccination. For instance, if an adverse event begins on the day of the study vaccination but prior to administration of the vaccine, it will be assigned to this dose. In case a study dose is not administered and an event occurs after the

204487 (ZOSTER-059 PRI) Statistical Analysis Plan Amendment 3

subsequent study dose (e.g. 2nd study dose), the associated dose of the event will be study dose associated to the subsequent study dose (e.g. dose 2).

The number of doses for a product is the number of times the product was administered to a subject.

The incidence per dose is the number of visits with vaccine administered at which an event was reported among all visits with vaccine administered.

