	Local adverse events										
Overall/dose	Any adverse event										
	General adverse events										
	Local adverse events										
Overall/subject	Any adverse event										
•	General adverse events										
	Local adverse events										

Co-Ad = Dose 1: Prevenar 13+ HZ/su, Dose 2: HZ/su

Control = Dose 1: Prevenar 13, Dose 2: HZ/su, Dose 3: HZ/su

For each dose and overall/subject: N = number of subjects with at least one documented dose; n/% =

number/percentage of subjects presenting at least one type of adverse event

For overall/dose: N = number of documented doses; n/% = number/percentage of doses followed by at least one type of adverse event

95% CI = exact 95% confidence interval, LL = Lower Limit, UL = Upper Limit

204487 (ZOSTER-059 PRI) Statistical Analysis Plan Amendment 3

Template 17 Incidence of solicited local adverse events reported during the 7-day (Days 1-7) post-vaccination period by study vaccine following each dose and overall <Exposed Set>

						Co-A	d			(Contr	ol	
							95%	6 CI				95%	% CI
Dose	Adverse event	Product	Туре	N	n	%	LL	UL	N	n	%	LL	UL
Dose 1	Pain	HZ/su	All										
			Grade 2 or 3										
			Grade 3										
			Medical advice										
		Prevenar13	All										
			Grade 2 or 3										
			Grade 3										
			Medical advice										
	Redness (mm)	HZ/su	All										
	, ,		>50										
			>100										
			Medical advice										
		Prevenar 13	All										
			>50										
			>100										
			Medical advice										
	Swelling (mm)	HZ/su	All										
			>50										
			>100										
			Medical advice										
		Prevenar 13	All										
			>50										
			>100										
			Medical advice										
Dose 2													
Dose 3													
Overall/Dose													
Overall/Subject													
	Drayonar 12 - H7/	D 0 117	1.										

Co-Ad = Dose 1: Prevenar 13+ HZ/su, Dose 2: HZ/su

Control = Dose 1: Prevenar 13, Dose 2: HZ/su, Dose 3: HZ/su

For each dose: N = number of subjects with the corresponding documented dose; n/% = number/percentage of subjects reporting the type of adverse event at least once following the corresponding dose

For Overall/dose: N = number of documented dose; n/% = number/percentage of doses followed by at least one type of adverse event

For Overall/subject: N = number of subjects with at least one documented dose; n/% = number/percentage of subjects reporting the type of adverse event at least once

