95%CI= Exact 95% confidence interval; LL = lower limit, UL = upper limit

204487 (ZOSTER-059 PRI) Statistical Analysis Plan Amendment 3

Template 18 Incidence of solicited general adverse events reported during the 7day (Days 1-7) post-vaccination period following each dose and overall <Exposed Set>

					<each gr<="" th="">		</each>		
							5 % CI
Dose	Adverse event	Туре	N	n	%	LL	UL
Dose 1	Fatigue	All					
		Grade 3					
		Related					
		Grade 3*Related					
		Medical advice					
	Gastrointestinal symptoms	All					
		Grade 3					
		Related					
		Grade 3*Related					
		Medical advice					
	Headache	All					
		Grade 3					
		Related					
		Grade 3*Related					
		Medical advice					
	Myalgia	All					
		Grade 3					
		Related					
		Grade 3*Related					
		Medical advice					
	Shivering	All					
		Grade 3					
		Related					
		Grade 3*Related					
		Medical advice					
	Fever (Oral) (°C)	All (≥38.0)					
		>38.0					
		>38.5					
		>39.0					
		>39.5					
		>40.0					
		Related					
		>39.0*Related					
		Medical advice					
Dose 2							
Dose 3							
Overall/Dose							
Overall/Subject							
	/enar 13+ H7/su Dose 2: H7/su						

Co-Ad = Dose 1: Prevenar 13+ HZ/su, Dose 2: HZ/su

Control = Dose 1: Prevenar 13, Dose 2: HZ/su, Dose 3: HZ/su

For each dose: N = number of subjects with the corresponding documented dose; n/% = number/percentage of subjects reporting the adverse event at least once following the corresponding dose

For Overall/dose: N = number of documented dose; n/% = number/percentage of doses followed by at least one type of adverse event

For Overall/subject: N = number of subjects with at least one documented dose; n/% = number/percentage of subjects reporting the type of adverse event at least once

95%CI= Exact 95% confidence interval; LL = lower limit, UL = upper limit

204487 (ZOSTER-059 PRI) Statistical Analysis Plan Amendment 3

Template 19 Summary of temperature value by half degree increment taken by different routes reported during the 7-day (Days 1-7) postvaccination following each dose < Exposed Set>

						С	o-Ad				Co	ntrol	
							95	% CI				95	% CI
Dose	Symptom	Route	Type	N	n	%	LL	UL	N	n	%	LL	UL
Dose 1	Temperature (°C)	Oral	≥35.0										
			>35.5										
			>36.0										
			>36.5										
			>37.0										
			>37.5										
			>38.0										
			>38.5										
			>39.0										
			>39.5										
			>40.0										
		Axillary	≥35.0										
		,	>35.5										
			>36.0										

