,	Face injury (10050392)				
	Head injury (10019196)				
Skin and subcutaneous tissue disorders (10040785)	Miliaria (10027627)				

Co-Ad = Dose 1: Prevenar 13+ HZ/su, Dose 2: HZ/su

Control = Dose 1: Prevenar 13, Dose 2: HZ/su, Dose 3: HZ/su

At least one adverse event = at least one adverse event experienced (regardless of the MedDRA Preferred Term) N = number of administered doses

n/% = number/percentage of doses followed by the adverse event

95% CI = exact 95% confidence interval; LL = Lower Limit, UL = Upper Limit

204487 (ZOSTER-059 PRI) Statistical Analysis Plan Amendment 3

Template 41 Number and percentage of subjects reporting the occurrence of <serious adverse events, potential Immune Mediated Disease> classified by MedDRA Primary System Organ Class and Preferred Term from <first vaccination up to 30 days post last vaccination, from 30 days post last vaccination dose up to end of study, from first vaccination up to study end> <,including number of events><Exposed Set>

			(-Ad =			(trol =
				95% CI					95% CI	
Primary System Organ Class (CODE)	Preferred Term (CODE)	n*	n	%	LL	UL	n*	n ^c	% L	L UL
At least one adverse event										
Blood and lymphatic system disorders (10005329)	Leukocytosis (10024378)									
Cardiac disorders (10007541)	Acute myocardial infarction (10000891)									
	Atrial fibrillation (10003658)									
	Cardiac failure congestive									
	(10007559)									
	Tachycardia (10043071)									
	Ventricular tachycardia (10047302)									

Co-Ad = Dose 1: Prevenar 13+ HZ/su, Dose 2: HZ/su

Control = Dose 1: Prevenar 13, Dose 2: HZ/su, Dose 3: HZ/su

At least one adverse event = at least one adverse event experienced (regardless of the MedDRA Preferred Term)

N = number of subjects included in the considered cohort in each group

n/% = number/percentage of subjects reporting the adverse event at least once

n* = **n**umber of events reported

95% CI = exact 95% confidence interval; LL = Lower Limit, UL = Upper Limit

Please note that n* will be used to present pIMD for CTRS posting.

Template 42 Global Summary of <serious adverse events, potential Immune
Mediated Disease> <with causal relationship with vaccination>
reported from <first vaccination up to 30 days post last vaccination,
from 30 days post last vaccination dose up to end of study, from
first vaccination up to study end> <Exposed Set>

	Co-Ad	Control	Total
Number of subjects with at least one <sae, pimd=""> reported</sae,>			

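### Safety tables put an exact 95% interval on pooled dose counts, although one subject can supply two or three of the doses

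*SAP*

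**What the plan says.** SAP 12.1.1 counts a dose as a vaccination visit and defines per-dose incidence by pooling visits over subjects: "The incidence per dose is the number of visits with vaccine administered at which an event was reported among all visits with vaccine administered". SAP 11 gives two such visits for Co-Ad and three for Control, the latter being "Dose 1: Prevenar 13, Dose 2: HZ/su, Dose 3: HZ/su".

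The shells in SAP 13.2 then attach an interval to those pooled counts:

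- **Template 16, Overall/dose rows.** Unit: "For overall/dose: N = number of documented doses; n/% = number/percentage of doses followed by at least one type of adverse event". Interval: "95% CI = exact 95% confidence interval, LL = Lower Limit, UL = Upper Limit".
- **Templates 17 and 18, Overall/dose rows.** The denominator is again documented doses. Interval: "95%CI= Exact 95% confidence interval; LL = lower limit, UL = upper limit".
- **Template 40, whole table.** The denominator is administered doses and the numerator reads "n/% = number/percentage of doses followed by the adverse event". Interval: "95% CI = exact 95% confidence interval; LL = Lower Limit, UL = Upper Limit".

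The text behind these tables, SAP 6.4.1, asks for less: "Total number/percentages of doses (per dose and overall) followed by AEs will be tabulated". It mentions no interval for doses, and Protocol 10.8 is the same. Neither document describes a clustered, robust or repeated-measures method for these rows.

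**The concern.** An exact binomial interval guarantees its coverage only for N independent trials with a single success probability. Pooled doses can break both conditions, and the two failures act in opposite directions.

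- **Correlation.** Someone who reacts at one visit may be more likely to react at the next. Positive correlation makes the pooled percentage more variable than binomial, so the interval is too narrow.
- **Unequal visit rates.** Control Dose 1 is Prevenar13 alone, while Doses 2 and 3 are HZ/su. If the rates differ by visit, the pooled count is less variable than a binomial count at the average rate, so the interval is too wide.

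What is at stake is the label. A reader of the report would take these intervals as having at least 95% coverage. The departure could also differ between arms, because Control pools three visits and Co-Ad two.

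**Working it through.** **Inputs from the documents.** 456 subjects per arm (SAP 2, Table 1). With full attendance that is 2 × 456 = 912 doses in Co-Ad and 3 × 456 = 1368 in Control. HZ/su rows have at most 2 doses per subject in either arm; Prevenar13 rows have one and are unaffected. Two-sided 95% (SAP 12.1.2).

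**Assumptions.** Clopper-Pearson limits: SAP 6.3.2 names that method for seropositivity and VRR, and the safety footnotes say only that the interval is exact. The within-subject correlation ρ and the visit rates are not in the documents, so ranges are used.

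**Step 1: the stated 95%, under independence.** Summing the exact distribution of the dose count over the values whose Clopper-Pearson limits contain the true rate, at rates of 5, 30 and 60%, gives coverage of 95.3-96.0% for both 912 and 1368 doses. The label is right in this case.

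**Step 2: equal visit rates, correlated visits.** With m doses per subject the variance is inflated by 1 + (m − 1)ρ, and coverage is roughly 2Φ(1.96/√[1 + (m − 1)ρ]) − 1. For ρ = 0.2 the inflation is 1.2 (m = 2) and 1.4 (m = 3), giving approximately 92.6% and 90.2%. Exact coverage, from a beta-binomial count per subject convolved over 456 subjects, at rates of 5, 30 and 60%:

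| ρ (assumed) | 2 doses | 3 doses |
|---|---|---|
| 0.1 | 94.2-95.0% | 93.0-93.9% |
| 0.2 | 93.0-93.9% | 90.7-91.7% |
| 0.5 | 89.5-90.7% | 84.0-85.2% |

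At a rate of 0.5%, as for a single Preferred Term in Template 40, coverage at ρ = 0.2 is 95.5% (2 doses) and 93.4% (3 doses).

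**Step 3: unequal visit rates in Control.** The ratio of the true to the assumed binomial variance is [Σpⱼ(1 − pⱼ) + 2ρΣⱼ<ₖ√(pⱼ(1 − pⱼ)pₖ(1 − pₖ))] / [3p̄(1 − p̄)]. For assumed rates of 20/80/80%, p̄ = 0.60. At ρ = 0 the ratio is (3 × 0.16)/(3 × 0.24) = 0.67, and exact coverage is 98.5%. For 30/75/75% at ρ = 0 the ratio is 0.81 and coverage 97.3%. Adding correlation, the normal approximation gives:

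| Control rates (assumed) | ρ = 0.05 | ρ = 0.1 | ρ = 0.2 |
|---|---|---|---|
| 50/75/75% | 94.6% | 93.6% | 91.3% |
| 30/75/75% | 96.2% | 95.3% | 93.4% |
| 20/80/80% | 97.8% | 97.2% | 95.8% |

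Simulation of the same cases agrees to within about 0.8 points. For 20/80/80% the largest possible correlation between Dose 1 and a later dose is √[(0.2 × 0.2)/(0.8 × 0.8)] = 0.25, so ρ = 0.2 is near the ceiling there.

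**Step 4: size on the percentage scale.** At a pooled rate of 30% with equal visit rates, the Clopper-Pearson limits are compared with a logit interval using variance p(1 − p)[1 + (m − 1)ρ]/N:

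| | Stated | Clustered, ρ = 0.2 | Clustered, ρ = 0.5 |
|---|---|---|---|
| 2 doses (N = 912) | 27.1-33.1% | 26.8-33.4% | 26.5-33.8% |
| 3 doses (N = 1368) | 27.6-32.5% | 27.2-32.9% | 26.7-33.5% |

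Each limit moves by at most about 0.5 points at ρ = 0.2 and 1.1 points at ρ = 0.5.

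**The case against.** The strongest reply is that this is a feature of mock shells, not of the planned analysis. Where the SAP text asks for exact intervals on adverse-event incidence, it asks for them on subjects; for doses it asks only for counts and percentages. SAP 13 says that displays and footnotes are illustrative and will be adapted following a table list that is not in these documents, so these interval cells may never be produced. The rows are descriptive, no decision uses them, and the percentages themselves are unaffected. The lowest coverage figures need a correlation of 0.5, for which there is no source, and for Control they also need equal rates at all three visits although Dose 1 is a different vaccine.

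Most of this stands, and it limits the point to a reporting correction. The correlations are assumptions, and the 84-85% figure should not be read as an expected value. But the illustrative status of the shells makes the correction easy; it does not make the interval right. As written, four templates pair a dose denominator with an exact label, and nothing else in the plan corrects that.

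Two further limits apply. The Overall/dose rows of Template 17 are blank in the shell, so splitting them by product is inferred from its title and Product column. Clopper-Pearson for the safety tables is likewise inferred.

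**Conclusion.** The point holds and is minor. On pooled-dose rows the exact 95% label is justified only if visits within a subject are independent and share one rate, and the design assures neither. Coverage may fall below or rise above 95%; the documents fix neither direction nor size. Over the assumed inputs it runs from about 84% (3 doses, equal rates, correlation 0.5) to about 98% (strongly unequal Control rates, little correlation). The movement of the limits at a 30% rate is about one percentage point or less. No co-primary conclusion, point estimate, single-dose row or overall/subject row is affected.

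**What to change.** Preferred: remove the interval wherever the denominator is doses and a subject can contribute more than one. That means the Overall/dose rows of Templates 16 and 18, the HZ/su Overall/dose rows of Template 17, and all of Template 40. Keep n and %. This matches SAP 6.4.1, and subject-level intervals remain in the per-dose and overall/subject rows of Templates 16-18 and in Templates 20, 26, 27 and 49. The cost is deleting some columns.

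If an interval is wanted in Templates 16-18, use a logit interval with variance clustered on subject and take the word *exact* out of the footnote. In simulation this covered 94.6-95.4% at event rates of 5% and above. It fails with very few events: at 3-5 events all misses fall on one side, and at zero events it is undefined. A cautious rule is to show it only when a row has at least 20 doses with and 20 without the event. This needs minor programming. Template 40 should still carry no interval.

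Do not substitute Clopper-Pearson on a reduced effective N. Using 456 subjects when there are no events gives an upper limit of 0.81%, above the 0.41% for one event and the 0.75% for four events in 1368 doses.

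Template 22 does not name its interval method; if it is binomial on doses, treat its Overall/Dose rows the same way. Leave the Prevenar13 rows of Template 17 as they are.

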Investigator safety reports are prepared according to the current GSK policy and are forwarded to investigators as necessary. An investigator safety report is prepared for a SAE(s) that is both attributable to the study vaccine(s) and unexpected. The purpose of the report is to fulfil specific regulatory and GCP requirements, regarding the product under investigation.

8.5. Follow-up of adverse events, serious adverse events, and pregnancies**8.5.1. Follow-up of adverse events and serious adverse events****8.5.1.1. Follow-up during the study**

After the initial AE/SAE report, the investigator is required to proactively follow each subject and provide additional relevant information on the subject's condition to GSK Biologicals (within 24 hours for SAEs; refer to [Table 22](#)).

All SAEs and pIMDs (serious or non-serious) documented at a previous visit/contact and designated as not recovered/not resolved or recovering/resolving will be reviewed at subsequent visits/contacts until the last visit of the subject.

All AEs documented at a previous visit/contact and designated as not recovered/not resolved or recovering/resolving will be reviewed at subsequent visits/contacts until 30 days after the last vaccination.

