4.2. Secondary endpoints

Occurrence of solicited local and general adverse events:

- Occurrence, duration and intensity of each solicited local adverse event within 7 days (Days 1 7) after each vaccination,
- Occurrence, duration, intensity and relationship to vaccination of each solicited general adverse event within 7 days (Days 1 7) after each vaccination.

Occurrence of unsolicited AEs:

Occurrence, intensity and relationship to vaccination of unsolicited AEs within 30 days (Days 1 - 30) after each vaccination, according to the Medical Dictionary for Regulatory Activities (MedDRA) classification.

Occurrence of SAEs:

- Occurrence and relationship to vaccination of all SAEs from first vaccination at Day 1 up to 30 days post last vaccination.
- Occurrence and relationship to vaccination of all SAEs during the period starting after 30 days post last vaccination up to study end.

Occurrence of pIMDs:

- Occurrence and relationship to vaccination of any pIMDs from first vaccination at Day 1 up to 30 days post last vaccination.
- Occurrence of any pIMDs during the period starting after 30 days post last vaccination up to study end.

204487 (ZOSTER-059 PRI) Statistical Analysis Plan Amendment 3

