6.4.2. Additional considerations

- The following additional tables will be generated:
 - The percentage of subjects with at least one local AE (solicited and unsolicited), with at least one general AE (solicited and unsolicited) and with any AE (solicited and unsolicited) during the 7-day follow-up period will be tabulated with exact 95% CI after each vaccine dose and overall. The same computations

204487 (ZOSTER-059 PRI) Statistical Analysis Plan Amendment 3

- will be done for Grade 3 AEs, for any AEs considered related to vaccination and for any Grade 3 AEs considered related to vaccination.
- The percentage of subjects with at least one local solicited AE, with at least one general solicited AE and with any solicited AE will also be done for Grade 3 solicited AEs, for any solicited AEs considered related to vaccination and for any Grade 3 solicited AEs considered related to vaccination.
- The percentage of subjects reporting each individual solicited local AE during the solicited 7-day follow-up period will be tabulated by study vaccine with exact 95% CI.
- Summary of temperature value by half degree increment taken by different routes reported during the 7-day (Days 1-7) post-vaccination following each dose.
- For fever, the number and percentage of subjects reporting fever by half degree (°C) cumulative increments during the 7-day follow-up period (Day 1-7) will be tabulated for each group after each vaccine dose and overall. Similar tabulations will be performed for Grade 3 (> 39.0°C) causally related fever.
- List of suspected HZ cases identified during the study will be presented.
- The number and percentage of subjects starting a concomitant medication during the 30-day post-vaccination period by dose and overall will be presented.
- The duration of solicited local adverse events (in days), not limited to the 7-day post-vaccination period, following each dose and overall/dose. The same tabulations after Prevenar13 and HZ/su vaccinations.
- The duration of solicited general adverse events (in days), not limited to the 7day post-vaccination period, following each dose and overall/dose.
- Solicited local adverse events ongoing beyond the 7-day (Days 1-7) post-vaccination period, following each dose and overall/dose. The same tabulations after Prevenar13 and HZ/su vaccinations.
- Solicited general adverse events ongoing beyond the 7-day (Days 1-7) post-vaccination period, following each dose and overall/dose.

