12.1.3. Safety

For a given subject and the analysis of solicited adverse event during the 7 day follow-up period after vaccination, missing or non-evaluable measurements will not be replaced. Therefore, the analysis of the solicited adverse events based on the ES will include only vaccinated subjects with documented safety data (i.e., symptom screen completed). More specifically the following rules will be used:

- Subjects who documented the absence of a solicited adverse event after one dose will be considered not having that adverse event after that dose.
- Subjects who documented the presence of a solicited adverse event and fully or
 partially recorded daily measurement over the solicited period will be included in the
 summaries at that dose and classified according to their maximum observed daily
 recording over the solicited period.

204487 (ZOSTER-059 PRI) Statistical Analysis Plan Amendment 3

- Subjects who documented the presence of a solicited adverse event after one dose
 without having recorded any daily measurement will be assigned to the lowest
 intensity category at that dose (i.e., 38°C for fever or grade 1 for other adverse
 events). The subject will only be presented in the subject with adverse event
 experienced and not in specific grade information.
- Doses without adverse event sheets documented will be excluded.

For analysis of unsolicited AEs, such as SAEs or adverse events by MedDRA Primary SOC and PTs term, and for the analysis of concomitant medications, all vaccinated subjects will be considered. Subjects who did not report the event or the concomitant medication will be considered as subjects without the event or the concomitant medication respectively.

Associated dose: The associated dose for an event (e.g., AE, medication, vaccination,...) is the study dose given before an event. In case the event takes place on a day a study dose is given, the associated dose will be that of the study dose even if the event actually took place before. For instance, for a conc. medication started on the day of study dose 2 but before dose 2 administrations, the associated dose will be dose 2

The way the percentage of subjects will be derived will depend on the event analysed (see the following table for details). As a result, the denominator (N) will differ from one table to another.

Event	N used for deriving %	Terminology used in the tables for N
Concomitant	All vaccinated subjects	Number of subjects with at least one

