50-59YOA = subjects aged 50-59 years; 60-69YOA = subjects aged 60-69 years; ≥70YOA = subjects aged 70 years and over

Template 39 Maximum intensity of solicited <local, general> adverse event ongoing beyond the 7-day (Days 1-7) post-vaccination period following each dose and overall <Exposed Set>

			Time to resolution	<each group> Value or</each 	<each group> Value or</each
Dose	Adverse event	Туре	(days)	n	n
<each dose=""></each>	<each adverse<="" td="">All	N	XX	XX	</each>	All	N	XX	XX
	event>		n	xx	XX
			q1	XX.X	XX.X
			median	XX.X	XX.X
			q3	XX.X	XX.X
		Grade 3	N	XX	XX
			n	XX	XX
			q1	XX.X	XX.X
			median	XX.X	XX.X
			q3	XX.X	XX.X
		Grade 3*Related	N	XX	XX
			n	xx	xx
			q1	XX.X	XX.X
DVERALL/DOSE			median	xx.x	XX.X
			q3	XX.X	XX.X
OVERALL/DOSE	<each adverse="" event<="" td="">><each type=""></each>	N	XX	XX	</each>	> <each type=""></each>	N	XX	XX
			n	XX	XX
			q1	XX.X	XX.X
			median	XX.X	XX.X
OVERALL/DOSE			q3	XX.X	XX.X

Co-Ad = Dose 1: Prevenar 13+ HZ/su, Dose 2: HZ/su

Control = Dose 1: Prevenar 13, Dose 2: HZ/su, Dose 3: HZ/su

Time to resolution: number of days beyond the end of the follow-up period N = number of adverse events that were ongoing after the follow-up period

n = number of adverse events that were ongoing after the follow-up period with a complete end date

q1 = 25th percentile; q3= 75th percentile

204487 (ZOSTER-059 PRI) Statistical Analysis Plan Amendment 3

Template 40 Number and percentage of doses reporting the occurrence of <grade 3> unsolicited adverse events classified by MedDRA Primary System Organ Class and Preferred Term <with causal relationship to vaccination> within the 30-day (Days 1-30) post-vaccination period <Exposed Set>

			ach I =	gr	oup
					5% CI
Primary System Organ Class (CODE)	Preferred Term (CODE)	n	%	LL	UL
At least one adverse event					
Gastrointestinal disorders (10017947)	Diarrhoea (10012735)				
, ,	Teething (10043183)				
	Vomiting (10047700)				
General disorders and administration site conditions (10018065)	Pyrexia (10037660)				
Immune system disorders (10021428)	Seasonal allergy (10048908)				
Infections and infestations (10021881)	Conjunctivitis (10010741)				
, ,	Otitis media (10033078)				
	Paronychia (10034016)				
	Tonsillitis (10044008)				
	Tonsillitis streptococcal (10044013)				
	Viral upper respiratory tract infection				
	(10047482)				
Injury, poisoning and procedural complications (10022117)	Arthropod bite (10003399)				

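### Template 39 in effect takes time to resolution beyond Day 7 only from events with a full end date, so any reaction unresolved at last review is dropped instead of censored

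*SAP*

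**What the plan says.** SAP Amendment 3, Section 6.4.2, lists among its additional safety tables a summary of solicited local and general events that outlast the diary period; for the general events it reads "Solicited general adverse events ongoing beyond the 7-day (Days 1-7) post-vaccination period, following each dose and overall/dose". Template 39 in Section 13.2 is the layout. For each dose, event and grade it prints two counts and three quartiles. One footnote defines the quantity being summarised: "Time to resolution: number of days beyond the end of the follow-up period". The larger count, N, takes in every event still open when the diary period closes, whether or not it has a date. The smaller count is restricted further: "n = number of adverse events that were ongoing after the follow-up period with a complete end date".

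The footnotes do not state which count feeds the quartiles. Section 12.1.3 says of the 7-day data that "missing or non-evaluable measurements will not be replaced"; the SAP has no rule for an end date after Day 7 that is absent or partial.

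Protocol Section 8.5.1.1 sets the follow-up. Unresolved SAEs and pIMDs are reviewed until the subject's last visit. Other unresolved adverse events "will be reviewed at subsequent visits/contacts until 30 days after the last vaccination".

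**The concern.** A time to resolution cannot be computed without an end date, so q1, median and q3 must come from the n dated events unless a rule says otherwise, and none does. A non-serious reaction still present at its last review has no end date. It is not a missing value: it is known to have lasted at least until that review, which makes it right-censored. Leaving it out removes information about the long tail, and the quartiles can then only move down.

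The follow-up limit runs from the last vaccination, not from each dose, so an event after an earlier dose can be observed for longer. The arms also number their doses differently. Dose 2 is the final vaccination in Co-Ad but the first of two HZ/su vaccinations in Control, so the side-by-side Dose 2 row compares data cut at different points. The overall/dose row mixes final and earlier doses in different proportions. At stake is a fair description of the most persistent reactions, in a trial whose secondary objective is safety and reactogenicity.

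**Working it through.** The plan gives no figure to reproduce here, and the mock table gives neither N nor n. What can be checked is the observation horizon, and how far dropping unresolved events would move the quartiles under stated assumptions.

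**1. Minimum horizon beyond Day 7.** Inputs: review ends 30 days after the last vaccination (Protocol 8.5.1.1); minimum intervals are 49 days between the HZ/su doses and 60 days from Prevenar13 to the first HZ/su dose in Control (Protocol Tables 8 and 9; SAP 5.1.4).

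- Final dose (Co-Ad Dose 2, Control Dose 3): 30 − 7 = 23 days.
- Dose before the last (Co-Ad Dose 1, Control Dose 2): 49 + 30 − 7 = 72 days.
- Control Dose 1: 60 + 49 + 30 − 7 = 132 days.

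These are minima. Protocol Tables 8 and 9 allow the visit after the last dose up to day 48; an end date collected there would stretch the final-dose horizon to 48 − 7 = 41 days.

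**2. Effect on the quartiles.** Assumption, not in the documents: residual time beyond Day 7 is exponential with mean m, and every event unresolved at horizon H is dropped. Then F = 1 − exp(−H/m) is the share kept. The true p-quantile is −m ln(1 − p); the reported one is −m ln(1 − pF).

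Worked case, m = 20 and H = 23: exp(−1.15) = 0.317, so 32% are dropped and F = 0.683. Reported median = −20 ln(1 − 0.342) = 8.4, against 13.9. Reported upper quartile = −20 ln(1 − 0.513) = 14.4, against 27.7.

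| Mean (days) | H (days) | Dropped | Median, reported vs true | Upper quartile, reported vs true |
|---|---|---|---|---|
| 5 | 23 | 1.0% | 3.42 vs 3.47 | 6.78 vs 6.93 |
| 10 | 23 | 10.0% | 6.0 vs 6.9 | 11.2 vs 13.9 |
| 20 | 23 | 31.7% | 8.4 vs 13.9 | 14.4 vs 27.7 |
| 20 | 41 | 12.9% | 11.4 vs 13.9 | 21.2 vs 27.7 |
| 20 | 72 | 2.7% | 13.3 vs 13.9 | 26.2 vs 27.7 |
| 20 | 132 | 0.1% | 13.8 vs 13.9 | 27.6 vs 27.7 |

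**3. Rows that mix horizons.** With the same true distribution in both arms and m = 20, the Dose 2 row would show an upper quartile of 14.4 in Co-Ad (H = 23) and 26.2 in Control (H = 72).

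For the overall/dose row, assume further that each dose contributes equally many ongoing events. Below 23 days, with k doses, the reported p-quantile t solves k(1 − exp(−t/m)) = p × (sum of F over doses).

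- Co-Ad: 0.683 + 0.973 = 1.656; 0.75 × 1.656 / 2 = 0.621; t = −20 ln(0.379) = 19.4 days.
- Control: 0.683 + 0.973 + 0.999 = 2.655; 0.75 × 2.655 / 3 = 0.664; t = −20 ln(0.336) = 21.8 days.

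With m = 5 the two overall/dose values are 6.86 and 6.88, which is no visible difference.

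**4. Bound without a distribution.** If a share c of the N events is undated and all of them outlast the dated ones, the reported p-quantile is really the p(1 − c) quantile of all N. At c = 10% the printed median sits at percentile 45 and the printed upper quartile at 67.5; at c = 30%, at 35 and 52.5. If dates are incomplete at random, nothing shifts.

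**The case against.** Four objections carry weight.

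- **Disclosure.** N stands directly above n in each cell, and individual listings of solicited events are planned (SAP 13.1), so the number left out is visible. That stands, but N − n mixes unresolved events with resolved events whose date is partial, and showing the count does not correct the quartiles.
- **Direction and size.** A reader might infer that the longest reactions are certainly lost and the quartiles certainly too short. The documents do not support that. The footnote also excludes resolved events with a partial date, which need not be long. The undated share is not given, and the bias is nil if nothing is unresolved.
- **Importance.** A reader might also infer that a secondary endpoint is affected. It is not: the endpoint is "Occurrence, duration and intensity of each solicited local adverse event within 7 days", and this table starts where that window ends. It is an additional descriptive output with no test attached.
- **Between-arm effect.** It is tempting to read the table as favouring co-administration. The comparison matched on the second HZ/su dose, Co-Ad Dose 2 against Control Dose 3, has the same horizon and the same visit window, so no arm-related truncation is shown there. The unequal truncation concerns the Dose 2 and overall/dose rows, and the Dose 2 row already sets different HZ/su doses side by side.

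Nor do the documents show the same exclusion in the related duration table, described as "The duration of solicited local adverse events (in days), not limited to the 7-day post-vaccination period". Its layout, Template 23, counts doses with the event and mentions no end-date condition; its handling of open events is simply unstated.

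**Conclusion.** The point holds as a conditional one of low severity. Template 39 has no rule for events unresolved at last review, and as laid out it can only summarise dated events. If any reaction is unresolved, the median and upper quartile understate time to resolution. Any material effect is confined to the final dose and to rows that include it; a horizon of 72 days or more costs little even at a mean of 20 days.

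The size cannot be fixed from the documents. Under the exponential assumption and the minimum 23-day horizon it runs from a shift of at most 0.15 days (mean 5) to a loss of 5.5 days in the median and 13.4 in the upper quartile (mean 20). Those means are illustrations with no anchor in the protocol or SAP. No co-primary conclusion and no 7-day endpoint changes.

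**What to change.** In Template 39, estimate q1, median and q3 by Kaplan-Meier on all N events for each dose, event and grade, censoring unresolved events at their last assessment. Print two counts in place of the single gap between N and n: events unresolved at last review, and events resolved with a partial or missing date. State in Section 12.1.3 how the second kind is handled. A sentence there should also say how open events enter the durations in Section 6.4.2 that run past Day 7.

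The cost is SAP wording and minor programming on data already collected. Some upper quartiles may have to be reported as not reached: once about a quarter of the events are censored at the end, that quartile cannot be estimated.
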